###### **The proportion of subjects requiring supplemental oxygen or non-invasive ventilation at any point during the study in subjects who did not require supplemental oxygen at baseline**

Number and the percentage of subjects requiring supplemental oxygen or noninvasive ventilation during the study in subjects who did not require supplemental oxygen at baseline will be summarized by treatment groups. Cochran Mantel-Haenszel test will be used to compare the treatment difference.

A by-subject listing will also be provided for subjects requiring supplemental oxygen or non-invasive ventilation.

###### **Time from randomization to defervescence**

Time from randomization to defervescence will be analyzed in subjects who had fever (body temperature of  $\geq 37.6^{\circ}\text{C}$  axilla,  $\geq 38.0^{\circ}\text{C}$  oral, or  $\geq 38.6^{\circ}\text{C}$  tympanic or rectal) at baseline. Defervescence is defined as body temperature of  $< 37.6^{\circ}\text{C}$  axilla,  $< 38.0^{\circ}\text{C}$  oral, or  $< 38.6^{\circ}\text{C}$  tympanic or rectal without taking any antipyretic treatment and sustained until discharge or Day 28. Time from randomization to the first defervescence event will be analyzed using KM method by treatment groups in subjects who had fever at baseline. A summary table of the number of events, the number of censors, and KM estimates (25th, 50th, 75th percentile of time to defervescence along with the 95% CI), and the defervescence rate at Day 7, Day 14, and Day 28 will be provided.

Hazard ratio and corresponding two-sided 95% CIs will be estimated using a Cox proportional hazards model, with treatment arm as a single covariate, stratified by the stratification factors.

A KM plot by treatment groups will be provided for time from randomization to defervescence and a by-subject listing will also be provided.

**Time from randomization to respiratory rate  $\leq 24$  breaths/minute on room air**

Respiratory rate  $\leq 24$  breaths/minute on room air and sustained until discharge or Day 28 will be considered as achieving the respiratory rate normalization event. Time from randomization to the first date of achieving normalization of respiratory rate will be analyzed using KM method by treatment groups. A summary table of the number of events, the number of censors, and KM estimates (25th, 50th, 75th percentile of time to normalization of respiratory rate along with the 95% CI), and the rate of normalization of respiratory rate at Day 7, Day 14, and Day 28 will be provided.

Hazard ratio and corresponding two-sided 95% CIs will be estimated using a Cox proportional hazards model, with treatment arm as a single covariate, stratified by the stratification factors.

A KM plot by treatment groups will be provided for time from randomization to respiratory rate normalization and a by-subject listing will also be provided.

**Time from randomization to cough reported as mild or absent (on a scale of severe, moderate, mild, absent, in those with cough at enrollment rated as severe or moderate)**

Time from randomization to cough relief will only be analyzed in subjects with cough self-reported as severe or moderate at baseline on a scale of severe, moderate, mild, or absent. Cough relief event is defined as subjects with cough self-reported as severe or moderate at baseline and reported as mild or absent during the study and sustained until discharge or Day 28. Time from randomization to the first date of achieving cough relief event will be analyzed using KM method by treatment groups. A summary table of the number of events, the number of censors, and KM estimates (25th, 50th, 75th percentile of time to cough relief along with the 95% CI), and the cough relief rate at Day 7, Day 14, and Day 28 will be provided.

Hazard ratio and corresponding two-sided 95% CIs will be estimated using a Cox proportional hazards model, with treatment arm as a single covariate, stratified by the stratification factors.

A KM plot by treatment groups will be provided for time from randomization to cough relief and a by-subject listing will also be provided.

**Time from randomization to dyspnea reported as mild or absent (on a scale of severe, moderate, mild, absent, in those with dyspnea at enrollment rated as severe or moderate)**

Time from randomization to dyspnea relief will only be analyzed in subjects with dyspnea self-reported as severe or moderate at baseline on a scale of severe, moderate, mild, or absent. Dyspnea relief event is defined as subjects with dyspnea self-reported as severe or moderate at baseline and reported as mild or absent during the study and sustained until discharge or Day 28. Time from randomization to the first date of achieving dyspnea relief event will be analyzed using KM method by treatment groups. A summary table of the number of events, the number of censors, and KM estimates (25th, 50th, 75th percentile of time to dyspnea relief along with the 95% CI), and the dyspnea relief rate at Day 7, Day 14, and Day 28 will be provided.

Hazard ratio and corresponding two-sided 95% CIs will be estimated using a Cox proportional hazards model, with treatment arm as a single covariate, stratified by the stratification factors.

A KM plot by treatment groups will be provided for time from randomization to dyspnea relief and a by-subject listing will also be provided.

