7. STUDY ASSESSMENT AND PROCEDURES

7.1. Schedule of Events and Study Parameters

Table 3: Schedule of Events

Assessment/Activity	Screening	Day		Treatm	ent Peri	iod		Follow-up		Notes
		1	Days 2-6	Day 7	Days 8-13	Day 14/ EOT	Days 15-27	Day 28/ EOS	Day 60 ±3	Screening and Day 1 should occur within a 1-day period; where they occur on the same day, assessments need not be repeated. Subjects remaining in hospital will undergo the assessments specified. All subjects will undergo the assessments specified for Day 14, Day 28, and Day 60 even if they are discharged from the hospital prior to Day 28.
Informed consent	X									
Medical history	X									
WHO ordinal scale assessment	X									(WHO 2020)
Pregnancy test	X							Х	X	WOCBP only. Pregnancy test can be serum βHCG or urine. The Day 60 test should be taken at home and self-reported during telephone contact.
Vital signs	X	X	X	Х	X	X	X	Х		Vital signs will include oxygen saturation daily for primary endpoint assessment in addition, temperature, respiratory rate, and blood pressure will also be assessed.
Cough and dyspnea assessments	Х	Х	X	Х	Х	Х	X	Х		Cough and dyspnea are assessed daily on a patient reported scale of severe, moderate, mild, or absent.
Body weight and height	X									
Physical examination	X	X	X	X	X	X		X		Full physical examination (including a minimum of general appearance, head, eyes, ears, nose, mouth, throat, heart, thyroid, chest and lungs, abdomen, extremities, neuromuscular system, skin, and lymph nodes) will be completed during screening; at all other timepoints the examination will be targeted.

Assessment/Activity	Screening	Day						Follow-up		Notes
		1 -	Days 2-6	Day 7	Days 8-13	Day 14/ EOT	Days 15-27	Day 28/ EOS	Day 60 ±3	Screening and Day 1 should occur within a 1-day period; where they occur on the same day, assessments need not be repeated. Subjects remaining in hospital will undergo the assessments specified. All subjects will undergo the assessments specified for Day 14, Day 28, and Day 60 even if they are discharged from the hospital prior to Day 28.
Chest X-ray	X					X				X-ray taken within 24 hours prior to Screening will be accepted. CT scan will be accepted in place of the X-ray if taken with 48 hours prior to Screening.
Nasopharyngeal swab		X	X	X		X		X		Nasopharyngeal swab will be taken on Days 1, 2, 4, 7, 14, and 28.
Hematology, coagulation, and clinical chemistry assessment	Х	Х	Х	Х	Х	Х		Х		Assessments taken within 24 hours prior to Screening will be accepted.

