### 3. STUDY DESIGN

#### 3.1. Overall Design

This is a randomized, double-blind, placebo-controlled, multicenter, Phase 2/3, 28-day study with safety follow-up by telephone call at Day 60. The study is designed to evaluate the efficacy and safety of PTC299 as compared with placebo in hospitalized adult subjects with confirmed pneumonia, diagnosed with COVID-19, and not requiring mechanical ventilation. All subjects regardless of receiving PTC299 or placebo, will also receive standard of care as defined per local written policies or guidelines. Eligible subjects will be equally (1:1) randomized to one of the two following treatment arms:

Arm A - Subjects in arm A will receive PTC299 200mg twice a day (BID) (morning and evening at approximately 12-hour intervals) on Days 1 to 7 followed by 50 mg QD (in the morning) on Days 8 to 14. Subjects will be followed up to Day 28 with a safety follow-up phone call at Day 60.

Arm B - Subjects in arm B will receive the matching placebo BID (morning and evening at approximately 12-hour intervals) on Days 1 to 7 followed by the matching placebo QD (in the morning) on Days 8 to 14. Subjects will be followed up to Day 28 with a safety follow-up phone call at Day 60.

Randomization will be stratified by the following three stratification factors:

- Age ( $\leq 62$  vs  $> 62$ )
- Remdesivir use (yes vs no)
- Dexamethasone use (yes vs no)

The study is expected to enroll approximately 380 subjects with two planned interim analyses. The first interim analysis is planned when approximately 40 randomized subjects (20 in each arm) have been enrolled and followed to Day 28 or discontinued due to death, or withdrawal consent, or lost-to-follow-up to assess the safety of the study drug. The 2nd interim analysis is planned when approximately 163 events have been observed (approximately 190 subjects have been followed up to 28 days) to assess the futility of the study.

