### 3.5. Stratification, Randomization, and Blinding

Randomization will occur at each subject's baseline (screening) visit using an Interactive Response Technology (IRT) system. Assignment to treatment groups is determined by a computer-generated random sequence. Randomization will be stratified by the following three stratification factors:

- Age ( $\leq 62$  vs  $> 62$ )
- Remdesivir use (yes vs no)
- Dexamethasone use (yes vs no)

This is a double-blind study. PTC personnel who are directly involved in the conduct of the study will remain blinded until the final database lock. Dummy treatment codes will be used for programming and review before final database lock.

The unblinded interim analyses will be conducted by an independent statistician and the results will be only shared in the closed session of the DSMB. The study team will be kept blinded for results related to the interim analyses.

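### The cough-relief and dyspnea-relief Cox models leave out baseline symptom grade, which is recorded and sets how far a subject must improve; adjusting for it would modestly sharpen both hazard ratios

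*SAP*

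**What the plan says.** SAP 4.9.2.1 defines both analysis sets by baseline grade: "Time from randomization to cough relief will only be analyzed in subjects with cough self-reported as severe or moderate at baseline" and, likewise, "Time from randomization to dyspnea relief will only be analyzed in subjects with dyspnea self-reported as severe or moderate at baseline". For both symptoms the event is a grade "reported as mild or absent during the study and sustained until discharge or Day 28".

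For each endpoint the hazard ratio is "estimated using a Cox proportional hazards model, with treatment arm as a single covariate, stratified by the stratification factors". SAP 3.5 names the factors (age at a cut of 62, remdesivir use, dexamethasone use); symptom grade is not among them.

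The grade is available. Protocol Table 3 and SAP Table 2 mark the symptom assessment at Screening and Day 1, and the Protocol note reads "Cough and dyspnea are assessed daily on a patient reported scale of severe, moderate, mild, or absent".

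Nothing else in the SAP uses it. The baseline list in 4.5.2 includes initial COVID-19 symptoms but not their grade. The sensitivity analyses in 4.9.1.1 and the subgroups in 4.11 concern only the primary endpoint.

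**The concern.** The scale runs severe, moderate, mild, absent, and the event is reaching mild or absent. A subject who starts at moderate is one grade away and a subject who starts at severe is two. Baseline grade thus measures the distance to the event. The models pool the two grades, and randomization does not balance them within these subsets.

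When a Cox model omits a prognostic covariate and the treatment has an effect, the estimated hazard ratio lies nearer 1 than the covariate-adjusted one, and power falls. A chance difference between arms in the severe share also adds noise that adjustment would remove. As planned, such a difference need not appear in any table. These ratios will be read inferentially: SAP 4.9 calls for p-values and 95% confidence intervals with point estimates, and SAP 4.1 sets a nominal 0.05 level.

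**Working it through.** **The plan's own figures.** The documents give no effect size, event count or power for cough or dyspnea relief. The only design effect is for the primary endpoint (SAP 3.6), and I borrow it as an assumption. It reproduces:
- Hazard ratio from the medians: 11/8 = 1.375, against 1.38 stated.
- Day 28 rates: 1 − 2^(−28/11) = 0.829 and 1 − 2^(−28/8) = 0.912, as stated.
- Power with 326 events: Φ(½·√326·ln 1.38 − 1.96) = Φ(0.948) = 82.8%, consistent with the stated more than 80%.

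**Assumptions, none from the documents.** Severe share p = 20 to 50%. Relief hazard, severe versus moderate, r = 0.33 to 1.0. Grade-adjusted treatment hazard ratio 1.38. Overall placebo median 11 days. Exponential times cut at Day 28.

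**Limit of the hazard ratio without grade.** With h = 1 (placebo) or 1.38 (PTC299), each arm is a mixture S(t) = (1−p)·exp(−λht) + p·exp(−λrht), with density f(t). The limiting log hazard ratio β solves ∫₀²⁸ [f₁ − (f₀+f₁)·S₁e^β/(S₁e^β+S₀)] dt = 0. The loss is 1 − β/ln 1.38.

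| r | HR without grade (p = 50% to 20%) | loss of log HR |
|---|---|---|
| 1.0 | 1.380 | 0% |
| 0.8 | 1.376 to 1.378 | under 1% |
| 0.67 | 1.368 to 1.372 | 2 to 3% |
| 0.5 | 1.347 to 1.358 | 5 to 8% |
| 0.4 | 1.326 to 1.344 | 8 to 12% |
| 0.33 | 1.307 to 1.330 | 11 to 17% |

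Example: p = 35%, r = 0.5 gives 1.349, and 1 − 0.299/0.322 is about 7%. With a true hazard ratio of 1.0 the limit is 1.000, so nothing is lost.

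**Power, stratified Cox with 8 strata (2×2×2), without → with grade.**
- True hazard ratio 1.38, 1,500 runs per setting. n = 250: 60% → 62% (p = 35%, r = 0.67), 60% → 64% (35%, 0.5), 45% → 60% (50%, 0.33). n = 150: 39% → 40%, 38% → 41%, 29% → 39%.
- True hazard ratio 1.375, p = 35%, times rounded up to days, 500 runs per setting, r = 0.4, 0.55, 0.7. n = 120: gains of 5.0, 1.2, 1.0 points. n = 190: 2.0, 2.4, 2.2. n = 260: 7.6, 3.4, 1.4.
- True hazard ratio 1.0: rejection stays at about 4 to 6% with or without grade.

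**Two-step mechanism.** Letting severe subjects pass through two sequential steps instead of having a constant hazard ratio (n = 150 to 250, p = 20 to 50%, 300 runs per setting), adjustment moved the average hazard ratio away from 1 by about 0.04 to 0.05 and raised power by about 4 to 8 points.

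**Chance imbalance.** The SD of the arm difference in severe share is √(4p(1−p)/n). At n = 190 and p = 35% this is √(4·0.35·0.65/190) = 6.9 points. A one-SD imbalance shifts the log hazard ratio by about 0.069·|ln r|: 0.063, 0.041 and 0.025 for r = 0.4, 0.55 and 0.7. The standard error, taking 85% of subjects with events, is 2/√(190·0.85) = 0.157.

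**The case against.** The strongest reply is that this is a modelling preference. Treatment as the only covariate, stratified by the randomization factors, is used consistently for the primary and secondary time-to-event endpoints and is valid under randomization. That stands: nothing here invalidates the planned hazard ratio.

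A reader might infer that the planned hazard ratios are biased toward 1. The documents do not support that. Attenuation needs a real treatment effect and a prognostic grade, and neither is quantified. The unadjusted ratio is a valid marginal estimate, so the adjusted one is a different estimand and not the truth restored. Nor is chance imbalance bias: a shift of 0.025 to 0.063 against a standard error near 0.16 is sampling variability that the confidence interval already covers.

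The gains are also small and partly noisy. Seven of the nine 500-run gains are 3.4 points or less, and each rejection rate has a Monte Carlo standard error of about 2 points. The direction is nonetheless the same in every setting and in both sets of runs.

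A further objection is that two sequential steps imply a delay, not proportional hazards. The two-step simulation addresses this, and the gain remains.

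The stakes are limited. Success rests on the primary endpoint alone. Protocol 8.4.3 plans only Kaplan-Meier summaries for these endpoints, and the SAP adds the hazard ratio without naming a comparison test for either.

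**Conclusion.** The point holds as a modest gain in efficiency, not as a validity failure. A recorded variable that selects the analysis set and fixes the distance to the event is left out of both models. If treatment works and grade is prognostic, the unadjusted hazard ratio is nearer 1 and less powerful than the adjusted one.

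With relief hazards of about 0.4 to 0.8 for severe versus moderate, the loss is roughly 1 to 10% of the log hazard ratio (up to 12% at 0.4 with half the set severe) and about 1 to 8 points of power. Larger losses, such as the 15 points at n = 250, appear only when severe subjects recover at a third of the moderate rate. With no treatment effect there is no attenuation. All of this rests on assumed severe shares, grade effects and set sizes, and on an effect size borrowed from the primary endpoint.

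Two extensions should not be drawn. A raw baseline temperature term for defervescence does not follow, because SAP 4.9.2.1 sets different fever thresholds by route (37.6°C axilla, 38.0°C oral, 38.6°C tympanic or rectal), so raw readings are not comparable. The primary analysis, with its 326 events and 380 subjects, is untouched.

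**What to change.** Before database lock, amend SAP 4.9.2.1 so that the stratified Cox models for cough relief and dyspnea relief include baseline grade of that symptom (severe versus moderate) as a covariate, using the same baseline value that places the subject in the set. A covariate is preferable to a further stratification factor, which would split the 8 strata again. Keep the treatment-only model as supportive, and add each symptom's baseline grade by arm to the tables in 4.5.2. Make no corresponding change for defervescence.

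The cost is a sentence or two in the SAP, one model term and one table row per symptom, with no new data. There is one small downside: the adjusted hazard ratio is conditional on grade while the Kaplan-Meier medians, rates and plots beside it stay unadjusted, so the table footnotes should say so. Specifying this before unblinding matters, since an adjustment chosen afterwards would carry little weight.

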3. STUDY DESIGN

3.1. Overall Design

This is a randomized, double-blind, placebo-controlled, multicenter 28-day study, with a safety follow-up telephone call at Day 60.

The study population is hospitalized adult subjects with confirmed pneumonia, diagnosed with COVID-19, and not requiring mechanical ventilation. For the purposes of enrollment of subjects into the study, "hospitalized patients" will include any COVID-19 patient either admitted or under observation in the hospital for a continuous period of 24 hours or more who otherwise fulfills the eligibility criteria.

Subjects will be randomized 1:1 to PTC299 treatment or placebo using a central randomization process, with approximately 190 subjects in each cohort. The randomization will be stratified by age (≤62 vs >62), remdesivir use (yes vs no), and dexamethasone use (yes vs no). All subjects will also receive standard of care (SOC), defined as the SOC per local written policies or guidelines. The use of steroids (except dexamethasone), sensitive CYP2D6 substrates, CYP2C inducers, IL-6 neutralizing antibodies, IL-6 receptor inhibitors, and any investigational therapies are prohibited.

Following eligibility screening and enrollment, subjects will receive oral tablets containing PTC299 or matching placebo 200 mg twice daily (BID) (morning and evening) on Days 1 to 7 and 50 mg once daily (QD) in the morning on Days 8 to 14.

Approximately 40 subjects (20 in each arm) will be enrolled initially, enrollment will then halt, and an interim analysis will be performed to assess safety. No formal statistical testing will be performed at the interim analysis. An independent data safety monitoring board (DSMB) and an independent HAC will review available data for the 40 subjects. Enrollment will continue if there are no safety concerns.

A second interim analysis is planned to assess futility. It will be performed when 50% of respiratory improvement events have been reached, ie, 163 events have been observed (approximately 190 subjects).

Subjects will be assessed daily while hospitalized. All subjects will undergo efficacy, safety, and laboratory assessments as summarized in Table 3. There will be a follow-up telephone call at Day 60 to assess AEs, SAEs, and deaths.

For subjects who are discharged from the hospital prior to Day 28:

- If SpO₂ is <94%, SpO₂ measurements will be taken daily until Day 28
- Subject-reported assessments for cough and dyspnea will continue to Day 28

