7.2. Efficacy Assessments

All assessments will be in line with the site's COVID-19 assessment guidelines.

Fever (body temperature), respiratory rate, and SpO_2 will be monitored regularly throughout each day during hospitalization. If a subject has received an antipyretic, assessment of fever should occur ≥ 4 hours after administration of the antipyretic.

Cough severity and dyspnea will be assessed daily via subject-reported scales as severe, moderate, mild, or absent.

For subjects who are discharged from the hospital prior to Day 28:

- If SpO₂ is <94%, SpO₂ measurements will be taken daily until Day 28
- Patient-reported assessments for cough and dyspnea will continue to Day 28
- No other assessments will take place except for those specified at Day 14, 28 and Day 60 in the protocol.

For any subjects who are transferred to the Intensive Care Unit during the study, assessments per protocol should be performed wherever reasonably practicable.

Collection of blood, serum and nasopharyngeal swabs for assessment of cytokine levels, acute phase proteins, complete blood count, other laboratory parameters, and viral load will be performed by qualified and trained personnel during hospitalization, or after discharge at a medical facility as agreed by the medical monitor. Laboratory parameters assessed will include, but not be limited to, those in Table 4.

Table 4: Laboratory Parameters to be Assessed

Laboratory Assessments	Parameters
Nasopharyngeal swab	RPP ^a
Hematology	CBC count with WBC differential
Clinical Chemistry	Comprehensive metabolic panel to include:
Coagulation	aPTT PT/INR
Urinalysis	Blood Bilirubin Glucose Ketones pH Protein
Pregnancy (WOCBP only)	Urine or Serum βHCG [Reflective from Chemistry Sample]

Laboratory Assessments	Parameters
Others	Cytokines ^a
	Antibody titers ^a
	Acute phase proteins
	Ferritin
	• CRP
	D-dimer
	Cardiac troponin

Abbreviations: ALP, alkaline phosphatase; ALT, alanine aminotransferase; aPTT, activated partial thromboplastin time; AST, aspartate aminotransferase; βHCG, beta human chorionic gonadotropin; CBC, complete blood count; CRP, C-reactive protein; CPK, creatinine phosphokinase; GGT, gamma-glutamyl transpeptidase; INR, international normalized ratio; LDH, lactate dehydrogenase; PT, prothrombin time; RPP, respiratory pathogen panel; Tbili, total bilirubin; WBC, white blood cell; WOCBP, women of childbearing potential.

All laboratory parameters should be assessed prior to dosing on Day 1.

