### 3.4. Study Assessments and Procedures

Subjects will be assessed daily while hospitalized. All subjects will undergo efficacy, safety, and laboratory assessments as summarized in [Table 2](#). There will be a follow-up telephone call at Day 60 to assess AEs, serious AEs, and deaths.

For subjects who are discharged from the hospital prior to Day 28:

- If SpO2 is  $< 94\%$ , SpO2 measurements will be taken daily until Day 28
- Subject-reported assessments for cough and dyspnea will continue to Day 28
- No other assessments will take place except for those specified at Day 14, Day 28 and Day 60 in the protocol

A follow-up telephone call at Day 60 will be performed to assess AEs, serious AEs, and deaths. The Day 60 pregnancy test will be taken at home and self-reported during the telephone contact. All subjects will undergo the assessments specified for Day 14 and Day 28 (End of Study), and participate in the Day 60 telephone call, even if they are discharged from the hospital prior to Day 28.

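### Cough and dyspnea relief need only hold to discharge, although both symptoms are still scored to Day 28, so durability is tested over windows that depend on discharge

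*SAP*

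**What the plan says.** **Event rule.** SAP 4.9.2.1 limits each analysis to subjects with severe or moderate symptoms at baseline. Cough relief requires the symptom to be "reported as mild or absent during the study and sustained until discharge or Day 28". Dyspnea has the same rule in a parallel paragraph, which begins "Dyspnea relief event is defined as subjects with dyspnea self-reported as severe or moderate at baseline".

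**Event date.** "Time from randomization to the first date of achieving cough relief event will be analyzed using KM method by treatment groups"; dyspnea is handled alike. The outputs for each endpoint are Kaplan-Meier quartiles, relief rates at Days 7, 14 and 28, and a stratified Cox hazard ratio with its confidence interval.

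**Collection after discharge.** For subjects discharged before Day 28, SAP 3.4 states "Subject-reported assessments for cough and dyspnea will continue to Day 28", and protocol 7.2 states "Patient-reported assessments for cough and dyspnea will continue to Day 28". The note to the schedule of events (protocol 7.1) reads "Cough and dyspnea are assessed daily on a patient reported scale of severe, moderate, mild, or absent", and that row is marked in every column from Screening to Day 28.

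**Contrast with other measures.** For oxygen saturation after discharge, protocol 3.1 says "If SpO₂ is <94%, SpO₂ measurements will be taken daily until Day 28". For everything else, protocol 7.2 says "No other assessments will take place except for those specified at Day 14, 28 and Day 60 in the protocol".

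**Protocol endpoint.** Protocol 2.2.2 and 8.4.3 define both endpoints as time to the symptom being reported mild or absent, with no requirement that relief last. SAP section 5 declares no change from the protocol's planned analyses.

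**The concern.** A discharge cut-off is understandable where measurement stops at discharge. That is the position for saturation already at 94% or above, temperature and respiratory rate, none of which has a daily series afterwards. Cough and dyspnea are the two efficacy measures that the plan goes on collecting from every discharged subject, yet the SAP gives them the same cut-off. No rule says what a moderate or severe score after discharge does to an event already counted.

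Two things are at stake. First, the reported Day 28 relief rate is not a rate of relief held to Day 28. Second, the length of the durability test depends on a post-randomization event, discharge, which treatment may affect; duration of hospitalization is itself a secondary endpoint. If one arm leaves hospital earlier, fewer of its relapses can disqualify an event, even if the symptom course is the same in both arms. Protocol 5.1.2 has subjects discharged before Day 14 finish their tablets at home, so the ignored period can include the end of dosing as well as the off-drug follow-up.

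**Working it through.** **1. The plan's own figures.** None is given for cough or dyspnea. The primary-endpoint figures reproduce:
- Day 28 rates from exponential medians of 11 and 8 days: 1 − 2^(−28/11) = 0.829 and 1 − 2^(−28/8) = 0.912.
- Expected events: 190 × (0.829 + 0.912) = 331, against 326 required.
- Power at 326 events and hazard ratio 1.38: Φ(√326/2 × ln 1.38 − 1.96) = 82.8%.

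None of these depends on the cough or dyspnea rule.

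**2. Rule against data.**

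| Measure | Scores after an improved discharge | Durability required to |
|---|---|---|
| SpO₂, temperature, respiratory rate | no daily series | discharge or Day 28 |
| Cough, dyspnea | continue to Day 28 | discharge or Day 28 |

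Only the second row has a rule that stops before the data do.

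**3. Unequal windows.** If relief starts on day t and discharge is on day D, relief must hold for D − t days; for an inpatient at Day 28 it must hold for 28 − t. Take two subjects with relief from Day 7. One discharged on Day 14 is tested for 14 − 7 = 7 days; one still in hospital at Day 28 is tested for 28 − 7 = 21 days. If both return to severe on Day 20 and stay there, the first has an event dated Day 7 and the second has none.

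The rule may also be one-sided. Relief first reported after discharge and held to Day 28 could count as an event, while a relapse after discharge cannot remove one.

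**4. Illustrative size.** The documents give neither a relapse rate nor the number of subjects with moderate or severe symptoms at baseline, so the following inputs are assumptions:
- d, the share of relieved subjects discharged before Day 28: 0.80 to 0.95.
- u, the share of those whose relapse is unresolved at the last score: 0.05 to 0.20.

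The share of counted events that would fail a Day 28 rule is d × u: from 0.80 × 0.05 = 0.04 to 0.95 × 0.20 = 0.19. Borrowing the primary endpoint's Day 28 rates (unrounded) and multiplying by 1 − d × u:
- placebo: 0.829 becomes 0.796 down to 0.671;
- PTC299: 0.912 becomes 0.875 down to 0.738.

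A relapse that resolves by the last score would leave the Day 28 rate unchanged and only delay the event.

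**5. Illustrative hazard ratio.** This is a simulation with 200,000 subjects per arm, exponential medians of 11 and 8 days, d = 0.90, and unresolved relapsers censored at Day 28. Under the discharge rule the hazard ratio is 1.37. Under a Day 28 rule:

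| u placebo | u PTC299 | Hazard ratio |
|---|---|---|
| 5% | 5% | 1.33 |
| 10% | 10% | 1.30 |
| 20% | 20% | 1.25 |
| 5% | 15% | 1.07 |
| 15% | 5% | 1.59 |

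The medians are borrowed from another endpoint and the unequal relapse rates are invented. The table shows that the estimate can be sensitive to the rule, in either direction; it predicts nothing about this trial.

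**The case against.** The strongest reply is that the protocol endpoint has no durability condition. Judged against it, the SAP rule is already the stricter one, a relapse after first relief would not undo an event, and a Day 28 requirement moves further from the protocol. That stands as far as it goes: relief is overstated only relative to the SAP's own durability rule. But having added such a rule, the SAP should apply it over the period it observes, and section 5 should not say that nothing changed.

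Other points that stand:
- A reader might infer that earlier discharge brings events forward in time. The SAP does not support that: events are dated to first relief, and discharge decides only how long a relapse can disqualify.
- A reader might infer a definite overstatement of the relief rate. Without a relapse rate no figure can be given, and resolved relapses do not lower the Day 28 rate.
- Daily scoring after discharge is inferred. The saturation bullet says daily; the symptom bullet says only that scoring continues. The schedule's daily note makes daily scoring the natural reading, but its header ties the specified assessments to subjects still in hospital, plus Days 14, 28 and 60 for all.
- The rule does not say whichever of discharge and Day 28 comes first. That is the plain reading, but it is not written.
- A common cut-off keeps these endpoints comparable with fever and respiratory rate.

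The statement in SAP 4.9.1 that all recorded measurements will be used does not close the gap. It sits in the primary-endpoint section and does not alter the symptom event rule. The only pre-specified sensitivity analyses (SAP 4.9.1.1) also concern the primary endpoint.

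**Conclusion.** The mismatch holds. For cough and dyspnea the SAP sets a durability condition, stops applying it at discharge, and leaves later scores unable to undo an event. Durability is therefore tested over unequal, discharge-dependent windows, and between-arm differences in discharge timing can enter the Day 28 rate and the hazard ratio.

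The conclusion rests on reading the rule as whichever comes first and on post-discharge scores being collected as both documents state. Its size cannot be fixed from the documents; 4 to 19 events per 100 is an illustration under assumed inputs.

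The reach is limited to two secondary endpoints with Kaplan-Meier summaries and a Cox estimate but no named log-rank test. A reader might extend the point to the trial's main conclusion; nothing supports that, since the primary endpoint, sample size, alpha and futility boundary do not use these scores.

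**What to change.** In SAP 4.9.2.1, for cough and dyspnea only:

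1. Define relief as mild or absent and sustained through the last available score up to Day 28, counting scores after discharge. Date the event to the first day of that sustained period.
2. Show the until-discharge version as supportive. At minimum, keep the current definition, state that it means whichever comes first, and add the Day 28 version as a pre-specified sensitivity analysis.
3. Report by arm the number of post-discharge returns to moderate or severe (resolved and unresolved) and the number of missing post-discharge scores.
4. State in SAP section 5 that a durability condition was added to the protocol's cough and dyspnea endpoints.

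The cost is SAP wording and programming; the schedule already calls for the data. There are two drawbacks. Some post-discharge scores will be missing, so a subject with few home scores is still judged over a short window and some dependence on discharge remains; item 3 makes this visible. The definition will also differ from the fever and respiratory-rate endpoints, which the SAP can justify by the difference in what is collected after discharge.
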